## **13 PUBLICATION POLICY**

The Institution and Investigator shall be permitted to communicate and or/publish data from the study in a manner consistent with customary academic standards. However, copies of any proposed publication or summaries of any prepared presentation should be submitted to Eiger BioPharmaceuticals at least 30 days in advance of the submission of such proposed publication or presentation. Eiger BioPharmaceuticals shall have a 30-day period to object to the proposed presentation or publication in order to permit Eiger BioPharmaceuticals to identify and remove Eiger BioPharmaceuticals confidential information.

## **14 PROTOCOL AMENDMENTS AND MODIFICATIONS**

The investigator will ensure that the study is conducted in accordance with the procedures and evaluations described in this protocol. The sponsor is responsible for all protocol amendments and modifications, except those intended to reduce immediate risk to subjects. The sponsor is responsible for submitting protocol amendments to the appropriate government regulatory authorities. The investigator is responsible for submitting protocol amendments to the appropriate IRB or ethics committee. Approval by the IRB/EC will be obtained before changes are implemented.

**APPENDIX A: SCHEDULE OF ASSESSMENTS**

EVENT	Screening	Day 1	Day 2	Day 3	Day 7	Day 14	Day 28	Treat wk 8	Treat wk 12-48	Follow wk 4
visit number	1	2	3	4	5	6	7	8	9-18	19
Informed consent	X									
Comprehensive physical exam	X									
Inclusion/exclusion criteria	X									
Medical history	X									
Concomitant medications	X	X	X	X	X	X	X	X	X	X
Adverse events			X	X	X	X	X	X	X	X
Weight	X	X								
Height	X	X								
BMI calculation	X	X								
Brief physical exam		X		X	X	X	X	X	X	X
Vital signs	X	X	X	X	X	X	X	X	X	X
12 lead ECG pre/post-dose 	X	X	X				X			X
Liver biopsy (if needed) 	X									
Complete blood count	X	X		X	X	X	X	X	X	X
Chemistry panel	X	X		X	X	X	X	X	X	X
Thyroid function	X									
Pregnancy test (serum)	X									
Pregnancy test (urine)		X								X
HBV DNA, HDV RNA	X	HDV RNA	HDV RNA	HDV RNA						
Viral mutation analysis 		X	X		X	X	X	X	X	X
HIV serology	X									
Urinalysis (pre-dose)	X			X	X		X	X	X	X
Urine drug screen 	X									
PBMC Collection	X	X	X	X	X	X	X	X	X	X
HCV viral load (quant PCR)	X									
PK sampling (pre-/post-dose) 	X	X	X	X	X	X	X	X	X	
INR	X									
Study drug administration		X			X					
Dispense study drug		X			X		X	X	X	
Study drug accountability			X		X		X	X	X	

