### Study Design

This study is a phase II, randomized, open-label study up to 48 weeks of treatment with EBP-994 alone, or in combination with Norvir® and/or Pegasys® in subjects chronically infected with HDV genotype 1. The duration of the study for each subject will last approximately 11-55 weeks (up to three week screening period, 4-48 week treatment period and four week safety follow-up period. The duration of the entire study is anticipated to be approximately 45 months (first subject in to last subject out). The investigator is free to initiate licensed medications at any time point and decrease the dose of EBP-994 if deemed warranted for GI side effects.

This study will explore EBP-994 in four groups of treatments:

Group 1: EBP-994 (up to 600 mg daily dose) monotherapy

Group 2: EBP-994 (up to 200 mg daily dose) in combination with Norvir®

Group 3: EBP-994 (up to 600 mg daily dose) in combination with Pegasys®

Group 4: EBP-994 (up to 150 mg daily dose) in combination with Norvir® and Pegasys®

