## **4 ELIGIBILITY CRITERIA**

Up to 75 subjects chronically infected with HDV genotype 1 will be enrolled at a single University study site.

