### ***4.1 Inclusion Criteria***

A subject may be included in this study if he/she meets all of the following criteria:

1. Males or females, 18 to 65 years of age who are diagnosed with HDV by PCR
2. Chronic hepatitis D infection, genotype 1, documented by a positive anti-HDV Ab test at least of 6 months duration and detectable HDV RNA by PCR within 3 months to study entry

3. Liver biopsy within the last two (2) years (biopsy can be done at the Screening Visit)
4. Positive viral load of >100,000 copies/mL as measured by quantitative PCR
5. Electrocardiogram (ECG) shows no acute ischemia or clinically significant abnormality and a QT/QTc interval <450 milliseconds - using Bazett's correction:  $QTc = QT/RR^{0.5}$  (ICH Guidance E14 Clinical Evaluation of QT/QTc Interval Prolongation and Proarrhythmic Potential for Non-Antiarrhythmic Drugs)
6. Females of childbearing potential (intact uterus and within 1 year since the last menstrual period) should be non-lactating and have a negative serum pregnancy test. In addition, these subjects should agree to use one of the following acceptable birth control methods throughout the study:
  - a. abstinence
  - b. surgical sterilization (bilateral tubal ligation, hysterectomy, bilateral oophorectomy) six months minimum
  - c. IUD in place for at least six months
  - d. barrier methods (condom or diaphragm) with spermicide
  - e. surgical sterilization of the partner (vasectomy for six months)
  - f. hormonal contraceptives for at least three months prior to the first dose of study drug
7. Willing and able to comply with study procedures and provide written informed consent

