## **6.2 Study Visit 2 (Day 1) - Treatment Period**

This Study Visit marks the beginning of the twenty-four weeks treatment Period in which subjects will receive EBP-994 treatments (EBP-994 alone or in combination with Norvir® and/or Pegasys®). Subjects will be admitted to the unit on the morning of Day 1 in a fasted

state (nothing to eat or drink except water) and will receive a standard breakfast between 45 - 30 minutes prior to scheduled dosing time.

The following evaluations and procedures will be performed at Study Visit 1 (see Appendix A for summary):

1. Brief physical examination pre-dose (performed by a physician, nurse practitioner, physician's assistant or nurse). This includes weight and vital signs as well as HEENT, heart, lungs, abdomen and lower extremity.
2. Vital signs pre-dose and after the post-dose ECG (BP after being seated for 5 minutes, pulse, respiratory rate and temperature)
3. Concomitant medications will be recorded
4. Adverse events will be recorded
5. 12-Lead ECG
6. Randomization

Subjects will be randomized to one of the following groups:

Group 1: EBP-994 (up to 600 mg daily dose) monotherapy  
Group 2: EBP-994 (up to 200 mg daily dose) in combination with Norvir®  
Group 3: EBP-994 (up to 200 mg daily dose) in combination with Pegasys®  
Group 4: EBP-994 (up to 200 mg daily dose) in combination with Norvir® and Pegasys®

7. Laboratory studies (Pre-Dose) (non-fasting):
  - a. Serum chemistry panel, including liver function tests and albumin
  - b. Complete blood count (CBC with differential and platelet count)
  - c. Quantitative PCR for HDV viral load
  - d. Blood samples (plasma and serum) for viral mutation analysis, resistance phenotyping, and analysis of drug mechanism and treatment response. These analyses include molecular and genetic analysis of drug mechanism, viral/host factors influencing treatment response (e.g. genotype and subgenotype analysis, quasispecies analysis, determination of drug and potential metabolite levels in plasma).
  - e. Urinalysis
  - f. Urine pregnancy test (child-bearing females only)

- g. Blood sample for monitoring immunologic changes in peripheral blood mononuclear cells (PBMC).
- 8. Pharmacokinetic blood samples (at the following time points: 0-pre-dose, post dose: 15 min, 30 min, 60 min, 90 min, 2h, 2.5 h, 3 h, 4 h, ,6 h, 8, 10, 12 h) (for those subjects participating in the PK portion of this trial)
- 9. Dosing Instructions:  

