The container(s) of study drug(s) along with any unused drug dispensed at Study Visit 5 should be returned at this visit. Study personnel will perform drug accountability on the returned container(s) of study drug(s) to assess dosing compliance. A new container of drug will be dispensed at this visit to the subject. Subjects should be instructed to return all container(s) and any unused study medication at the next study visit. At each subsequent Study Visit, drug accountability will be performed for each subject to ensure that subject is compliant with dosing. Subjects should be instructed NOT to take their morning dose of study drug on the morning of the next Study Visit, Day 56, as pre-dose assessments will be conducted. Subjects should be sent home 3 hours post-dose, except for those participating in the PK component of the study.

If this is the last treatment visit, no new containers of drug(s) will be dispensed and all unused study medication will be collected.

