## **6.10 Study Visit 19 – Four Week Post-Treatment Follow-Up**

Same assessments are taken as in 6.9. No new containers of drug(s) will be dispensed. All unused study medication will be collected. No dosing at this visit.

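### No pregnancy test is scheduled between Day 1 and the 4-week follow-up, and the protocol body has no rule for a pregnancy that occurs on study

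*Combined protocol and SAP*

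**What the plan says.** **Entry.** Section 4.1 requires women of childbearing potential to be non-lactating and to have a negative serum pregnancy test. It adds that "these subjects should agree to use one of the following acceptable birth control methods throughout the study". Section 6.1 places the serum test at Screening.

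**Day 1.** Section 6.2 lists "Urine pregnancy test (child-bearing females only)" among the pre-dose laboratory studies, so this test comes before any exposure.

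**During dosing.** Sections 6.3 to 6.9 list no pregnancy test. Appendix A agrees: the row "Pregnancy test (urine)" is marked at Day 1 and follow-up week 4, and is blank from Day 2 to weeks 12-48.

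**Follow-up.** Appendix A marks a urine test. Section 6.10 says "Same assessments are taken as in 6.9", and 6.9 lists none.

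**Duration.** The Protocol Summary describes "up to three week screening period, 4-48 week treatment period and four week safety follow-up period".

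**If a pregnancy occurs.** Section 4.3 allows the investigator to withdraw a subject for a safety risk. Section 7.1.2 counts a birth defect as a serious outcome, with mandatory reporting for events during the study or up to 30 days after the last dose. Section 7.1 follows adverse events to resolution, and 7.2 follows subjects withdrawn for an adverse experience. None of these names pregnancy.

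**The concern.** The protocol treats fetal exposure as something to avoid: it requires contraception and counts birth defects as serious. Yet once dosing starts, no scheduled procedure would show that contraception had failed. A woman who conceives on treatment could go on taking EBP-994, with or without Norvir and Pegasys, and be given new supplies, until she or the investigator suspects pregnancy. Suspicion may come late. Nausea and vomiting are among the common side effects given in Section 7.3, so early symptoms could be put down to the drug; this is a clinical inference, not a statement in the protocol.

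When a pregnancy is found, the site has no instruction to stop drug, to report it, or to follow it to outcome. A birth defect recognised months after an on-treatment conception could fall outside the 30-day reporting window. A safety study would then lose information that it would want.

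**Working it through.** The plan states no figure on this point, so there is none to reproduce. The check compares the schedule with the visit text and counts.

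**Inputs**
- Treatment length T: 4 to 48 weeks (Protocol Summary, Study Design). Within that range, 12 weeks appears in the objectives (Section 2) and 24 weeks in Section 6.2.
- Follow-up: 4 weeks after treatment.
- Visits after Day 1: Days 2, 3, 7, 14 and 28, week 8, then 4-weekly from week 12 to week 48 (Visits 9-18, ten visits).
- Visit window: ±2 days, except Days 2 and 3.
- Sample: "Up to 75 subjects chronically infected with HDV genotype 1 will be enrolled at a single University study site".

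**Table against text.** The dosing-visit cells are blank in Appendix A, and Sections 6.3 to 6.9 list no test either. Two separate sources agree, so the blanks are not a table-reading artefact. At follow-up the two disagree: scheduled tests after Day 1 number 1 by Appendix A and 0 by Section 6.

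**Formulas**
- Gap between scheduled tests now (Appendix A) = T + 4 weeks.
- Treatment visits after Day 1 with no test = 4 early visits (Days 2, 3, 7, 14) + T/4.
- Tests added by the fix (Day 28, week 8, each later visit) = T/4.
- Added tests that come before further drug is dispensed = T/4 − 1. The last falls at the final treatment visit, where "If this is the last treatment visit, no new containers of drug(s) will be dispensed and all unused study medication will be collected".

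| Course (weeks) | Gap now (weeks) | Visits with no test | Tests added | Before further dispensing |
|---|---|---|---|---|
| 4 | 4 + 4 = 8 | 4 + 1 = 5 | 1 | 0 |
| 12 | 12 + 4 = 16 | 4 + 3 = 7 | 3 | 2 |
| 24 | 24 + 4 = 28 | 4 + 6 = 10 | 6 | 5 |
| 48 | 48 + 4 = 52 | 4 + 12 = 16 | 12 | 11 |

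**Gap after the fix.** Nominally 4 weeks. With windows, Day 1 to Day 30 is at most 29 days; between later visits the most is 28 + 2 + 2 = 32 days. The nominal gap shrinks by a factor of 8/4 = 2, 16/4 = 4, 28/4 = 7 or 52/4 = 13.

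**Is urine already there?** Yes. The Appendix A row "Urinalysis (pre-dose)" is marked at Day 28, week 8 and weeks 12-48, and Sections 6.7, 6.8 and 6.9 each list urinalysis before the dose.

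**Upper limit on strips.** 75 × 12 = 900, if every subject were a woman of childbearing potential treated for 48 weeks. The true number is lower, because men and women up to age 65 are eligible. Section 4.3 allows replacements and does not say whether they count within the 75, so 900 is approximate.

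**The case against.** The best case for the plan is that it already guards against pregnancy. Contraception is required for the whole study, not only at entry, and the listed methods include abstinence, sterilization and an established IUD. This safeguard is continuous and does not depend on anyone suspecting pregnancy. Women are also seen every 4 weeks after Day 28 with a brief examination and adverse event recording, and Section 6.11 allows extra tests for a specific concern. A reader might therefore infer from the missing tests that the protocol is silent on pregnancy or has no pregnancy rule at all. The documents do not support that: entry rules and two pre-dose tests are explicit. What is missing is a check during dosing and an instruction for a pregnancy on study.

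Three further objections carry some weight. The figures measure spacing between tests, not harm; no expected number of conceptions can be worked out. The 4-weekly interval follows the visit calendar rather than any stated risk, so a sparser schedule could also be defended. And consent pages are not part of the reviewed text, so instructions given to subjects cannot be judged.

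What remains is that contraception can fail, and the on-treatment means of detection (examination, adverse event recording, extra visits) work only once someone suspects pregnancy. The mismatch between 6.10 and Appendix A stands regardless.

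**Conclusion.** The point holds as a safety improvement that should be made. No pregnancy test is scheduled from the pre-dose Day 1 test to the 4-week follow-up: a gap of 8 weeks for the shortest course and 52 weeks for the longest, assuming Appendix A is followed. If Section 6.10 is followed instead, there is no test after Day 1. The protocol body has no rule to stop drug, report, or follow to outcome when pregnancy occurs on study.

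Two stronger readings should be resisted. One is that a 52-week gap is typical; it applies only to a 48-week course, and the documents do not say how many subjects receive each length. The other is that fetal risk is known to be high. Section 1.2 names a rabbit embryo-fetal study without giving its result, so the risk cannot be graded either way. The number of women of childbearing potential is also not given. No endpoint or statistical analysis is affected.

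Confidence is high for the schedule facts. The choice of 4-weekly testing rests on its very low cost at existing visits.

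**What to change.** 1. In Appendix A and Sections 6.7, 6.8 and 6.9, add a urine pregnancy test for women of childbearing potential at Day 28, week 8 and each week 12-48 visit. Use the urine already collected, and read the result before that visit's dose and before drug is dispensed.
2. In Section 6.10, list the follow-up urine pregnancy test that Appendix A marks.
3. In Section 4.3, state that study drug is stopped on a confirmed positive test. The present wording permits withdrawal for a safety risk but does not require it, so testing alone would leave the decisive step to discretion.
4. Secondary: in Section 7.1.2, require any pregnancy from first dose to end of follow-up to be reported to the Medical Monitor within 24 hours and followed to outcome. State that birth-defect reporting is not limited to 30 days after the last dose.

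**Cost.** 1 to 12 strips per woman of childbearing potential (about 900 in total at the very most), a pregnancy report form, a protocol amendment, and outcome follow-up for the few pregnancies that occur. No new visit, urine collection or blood draw.

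**Limit.** For 4-week subjects the added test brings detection forward by 4 weeks but does not shorten dosing, except that the final morning dose at Day 28 could be withheld.

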**Schedule of Assessments Footnotes**

**1 = Serial ECG (x3) 2 -3 minutes apart**

**2 = See Appendix 4 for CTP scoring and encephalopathy results**

**3 = Serum and plasma samples for viral mutation analysis, resistance phenotyping and analysis of drug mechanism and treatment response**

**4 = Urine drug screen for opiates, amphetamines, barbiturates, benzodiazapenes, cocaine**

**5= Timepoints for optional PK sampling pre-dose (0), 15 min, 30 min, 60 min, 90 min, 2h, 2.5h, 3h, 4h, ,6 h, 10h, 12h**

## APPENDIX B: BODY MASS INDEX TABLE (METRIC), FORMULA AND CALCULATOR

BMI	BMI TABLE																
	19	20	21	22	23	24	25	26	27	28	29	30	31	32	33	34	35
Height cms (metres)	Body Weight (kilograms)																
147cm (1.47m)	41	44	45	48	50	52	54	56	59	61	63	65	67	69	72	73	76
150cm (1.50m)	43	45	47	49	52	54	56	58	60	63	65	67	69	72	74	76	78
152cm (1.52m)	44	46	49	51	54	56	58	60	63	65	67	69	72	74	76	79	81
155cm (1.55m)	45	48	50	53	55	57	60	62	65	67	69	72	74	77	79	82	84
157cm (1.57m)	47	49	52	54	57	59	62	64	67	69	72	74	77	79	82	84	87
160cm (1.60m)	49	51	54	56	59	61	64	66	69	72	74	77	79	82	84	87	89
163cm (1.63m)	50	53	55	58	61	64	66	68	71	74	77	79	82	84	87	89	93
165cm (1.65m)	52	54	57	60	63	65	68	71	73	76	79	82	84	87	90	93	95
168cm (1.68m)	54	56	59	62	64	67	70	73	76	78	81	84	87	90	93	95	98
170cm (1.70m)	55	57	61	64	66	69	72	75	78	81	84	87	90	93	96	98	101
172cm (1.72m)	57	59	63	65	68	72	74	78	80	83	86	89	92	95	98	101	104
175cm (1.75m)	58	61	64	68	70	73	77	80	83	86	89	92	95	98	101	104	107
178cm (1.78m)	60	63	66	69	73	76	79	82	85	88	92	95	98	101	104	107	110
180cm (1.80m)	62	65	68	71	75	78	81	84	88	91	94	98	101	104	107	110	113
183cm (1.83m)	64	67	70	73	77	80	83	87	90	93	97	100	103	107	110	113	117
185cm (1.85m)	65	68	72	75	79	83	86	89	93	96	99	103	107	110	113	117	120
188cm (1.88m)	67	70	74	78	81	84	88	92	95	99	102	106	109	113	116	120	123
191cm (1.91m)	69	73	76	80	83	87	91	94	98	102	105	109	112	116	120	123	127
193cm (1.93m)	71	74	78	82	86	89	93	97	100	104	108	112	115	119	123	127	130
BMI	19	20	21	22	23	24	25	26	27	28	29	30	31	32	33	34	35

Use this BMI chart to calculate your Body Mass Index (BMI).

- First select your height then select your weight.
- Select the nearest value/s to your own if they are not displayed in the chart.
- Your BMI will be listed at the top and bottom of the BMI chart.

Source: <http://www.whathealth.com/bmi/chart-metric2.html>

### BMI FORMULA

$$\text{BMI} = \frac{\text{Weight in Kilograms}}{(\text{Height in centimeters}) \times (\text{Height in centimeters})}$$

For example a person who weighs 110 kgs and is 190.5 cm tall has a BMI of 30.3.

$$\frac{110 \text{ kgs}}{(190.5 \text{ cm}) \times (190.5 \text{ cm})} = 30.3$$

### BMI CALCULATOR

For additional information, including a BMI Calculator, please consult  
[www.whathealth.com/bmi/chart-metric.html](http://www.whathealth.com/bmi/chart-metric.html)

## **APPENDIX C: DECLARATION OF HELSINKI**

### **WORLD MEDICAL ASSOCIATION DECLARATION OF HELSINKI**

#### **Ethical Principles for Medical Research Involving Human Subjects**

Adopted by the 18th WMA General Assembly  
Helsinki, Finland, June 1964

And amended by the

29th WMA General Assembly, Tokyo, Japan, October 1975

35th WMA General Assembly, Venice, Italy, October 1983

41st WMA General Assembly, Hong Kong, September 1989

WMA General Assembly, Somerset West, Republic of South Africa, October 1996

52nd WMA General Assembly, Edinburgh, Scotland, October 2000

#### **A: INTRODUCTION**

1. The World Medical Association has developed the Declaration of Helsinki as a statement of ethical principles to provide guidance to physicians and other participants in medical research involving human subjects. Medical research involving human subjects includes research on identifiable human material or identifiable data.
2. It is the duty of the physician to promote and safeguard the health of the people. The physician's knowledge and conscience are dedicated to the fulfillment of this duty.
3. The Declaration of Geneva of the World Medical Association binds the physician with the words, "The health of my patient will be my first consideration," and the International Code of Medical Ethics declares that, "A physician shall act only in the patient's interest when providing medical care which might have the effect of weakening the physical and mental condition of the patient."
4. Medical progress is based on research which ultimately must rest in part on experimentation involving human subjects.
5. In medical research on human subjects, considerations related to the well-being of the human subject should take precedence over the interests of science and society.
6. The primary purpose of medical research involving human subjects is to improve prophylactic, diagnostic and therapeutic procedures and the understanding of the aetiology and pathogenesis of disease. Even the best proven prophylactic, diagnostic, and therapeutic methods must continuously be challenged through research for their effectiveness, efficiency, accessibility and quality.

7. In current medical practice and in medical research, most prophylactic, diagnostic and therapeutic procedures involve risks and burdens.
8. Medical research is subject to ethical standards that promote respect for all human beings and protect their health and rights. Some research populations are vulnerable and need special protection. The particular needs of the economically and medically disadvantaged must be recognized. Special attention is also required for those who cannot give or refuse consent for themselves, for those who may be subject to giving consent under duress, for those who will not benefit personally from the research and for those for whom the research is combined with care.
9. Research Investigators should be aware of the ethical, legal and regulatory requirements for research on human subjects in their own countries as well as applicable international requirements. No national ethical, legal or regulatory requirement should be allowed to reduce or eliminate any of the protections for human subjects set forth in this Declaration.

